### 11.3 Access to Data

Direct access will be granted to authorised representatives from the Sponsor, host institution and the regulatory authorities to permit trial-related monitoring, audits and inspections.

### 11.4 Archiving

Archiving will be authorised by the Sponsor following submission of the end of study report

The research group will be responsible for archiving all research data collected.

Paper archiving will be for 5 years from the end of the study and be based in a locked room in the Old Medical School, Leeds General Infirmary.

## 12 MONITORING, AUDIT & INSPECTION

- A Trial Monitoring Plan will be developed and agreed by the Trial Management Group (TMG) and TSC based on the trial risk assessment which may include on site monitoring
- It is not anticipated this pilot study will be monitored or inspected.
- Any authorised body will be supported by the trial site to in monitoring the study. These may include hosting site visits, providing information for remote monitoring, or putting procedures in place to monitor the study internally

## 13 ETHICAL AND REGULATORY CONSIDERATIONS

### 13.1 Research Ethics Committee (REC) review& reports

- Before the start of the trial, approval will be sought from a REC for the trial protocol, informed consent forms and other relevant documents.
- Substantial amendments that require review by REC will not be implemented until the REC grants a favourable opinion for the study (and/or NHS R&D departments before they can be implemented in practice at sites)
- All correspondence with the REC will be retained in the Trial Master File/Investigator Site File
- An annual progress report (APR) will be submitted to the REC within 30 days of the anniversary date on which the favourable opinion was given, and annually until the trial is declared ended
- It is the Chief Investigator's responsibility to produce the annual reports as required.
- The Chief Investigator will notify the REC of the end of the study
- If the study is ended prematurely, the Chief Investigator will notify the REC, including the reasons for the premature termination
- Within one year after the end of the study, the Chief Investigator will submit a final report with the results, including any publications/abstracts, to the REC

### 13.2 Peer review

### High quality peer review

Peer review has been completed by [name], Consultant Microbiologist, Leeds Teaching Hospitals NHS Trust.

### 13.3 Public and Patient Involvement

The involvement of Patients and Public in the research includes

- A previous design of this study was presented to the Leeds Cancer PPIR group. This resulted in a recommendation for an interventional trial as per this study.
- This study design (Colo-Pro) is due to be presented to this group again in June 2015.

### 13.4 Protocol compliance

Accidental protocol deviations will be adequately documented on the relevant forms and reported to the sponsor immediately.

### 13.7 Data protection and patient confidentiality

All investigators and trial site staff will comply with the requirements of the Data Protection Act 1998 with regards to the collection, storage, processing and disclosure of personal information and will uphold the Act's core principles.

This includes:

The creation of coded, depersonalised data where the participant's identifying information is replaced by an unrelated sequence of characters

Secure maintenance of the data and the linking code in separate locations using encrypted digital files within password protected folders and storage media

Limiting access to the minimum number of individuals necessary for quality control, audit, and analysis

The PI is the data custodian

### 13.8 Financial and other competing interests for the chief investigator, PIs at each site and committee members for the overall trial management

None to declare

### 13.9 Indemnity

#### The University of Leeds is providing

1. Insurance and/or indemnity to meet the potential legal liability of the sponsor for harm to participants arising from the management of the research.
2. Insurance and/ or indemnity to meet the potential legal liability of the sponsor or employer for harm to participants arising from the design of the research.

The NHS is providing

3. Insurance and/ or indemnity to meet the potential legal liability of investigators/collaborators arising from harm to participants in the conduct of the research.

The sponsor has not made arrangements for payment of compensation in the event of harm to the research participants where no legal liability arises.

### **13.10 Amendments**

Amendments will be agreed by the Trial management and data (safety) monitoring group. The Trial management and data (safety) monitoring group will decide if amendments are substantial.

An amendment history will be maintained in the trial master file.

HRA guidance on reporting of amendments (non CTIMP reporting) will be followed.

<http://www.hra.nhs.uk/resources/during-and-after-your-study/progress-and-safety-reporting/>

**13.11 Post trial care**

No post trial care is planned, or relevant to this trial.

**13.12 Access to the final trial dataset**

The trial management and data (safety) monitoring group will have access to the final data set.

**14 DISSEMINATION POLICY****14.1 Dissemination policy**

Consort Guidelines will be reviewed prior to generating any publications for the trial to ensure they meet the standards required for submission to high quality peer reviewed journals.

The data will be owned by The University of Leeds.

On completion of the trial, the data will be analysed and tabulated and a Final Study Report prepared where the full study report can be accessed

We plan to notify the participants of the outcome of the trial, by provision of the publication, and via a specifically designed newsletter.

**14.2 Authorship eligibility guidelines and any intended use of professional writers**

Authorship will include

On the final trial report: The Trial Steering Committee

For individually named authors: According to The International Committee of Medical Journal Editors definitions for authorship criteria for manuscripts submitted for publication.

**16. APPENDICIES**

**16.1 Appendix 1-Risk**

Risks associated with trial interventions

- LOW ≡ Comparable to the risk of standard medical care
- MODERATE ≡ Somewhat higher than the risk of standard medical care
- HIGH ≡ Markedly higher than the risk of standard medical care

Justification: Briefly justify the risk category selected and your conclusions below (where the table is completed in detail the detail need not be repeated, however a summary should be given):

The intervention antibiotic prophylaxis is an evidence based intervention.

The method of administering the intervention, continuous infusion, is an established method of intervention, and used routinely in many health care systems.

The maximum loading dose of cefuroxime recommended in this study, 2332 mg, is below the SPC single dose recommended for dosing cefuroxime of 3000mg.

The maximum total dose of cefuroxime recommended in this study, 9688mg over 6 hours, is comparable to that in the drug SPC for treating meningitis, 3000mg 8 hourly (6000mg infused in an 8 hour period).

Beta-lactam therapy is established as a safe treatment. High dose beta-lactam therapy is routinely administered e.g. 2400mg benzylpenicillin 4 hourly for treatment of endocarditis, amoxicillin 2000mg four hourly for endocarditis, flucloxacillin 2000mg 4 hourly for endocarditis, piperacillin 4000mg 8 hourly for severe infections.

What are the key risks related to therapeutic interventions you plan to monitor in this trial?		How will these risks be minimised?		
MP/Intervention	Body system/Hazard	Activity	Frequency	Comments
Cefuroxime	Gastrointestinal tract/Clostridium difficile associated diarrhoea	Routine clinical assessment	Continuous while a hospital in-patient	
Cefuroxime	Hepatobiliary disorders	Liver function test (blood)	Clinically driven testing	
Cefuroxime	Blood and lymphatic system disorders	Full blood count	Clinically driven testing	
Cefuroxime	Skin and subcutaneous tissue disorders	Routine clinical assessment	Continuous in-patient assessment	
Cefuroxime	Renal and urinary disorders	Renal function monitoring (blood tests)	Clinically driven testing	
Cefuroxime	General disorders and administration site conditions	Injection site reactions which may include pain and thrombophlebitis	Routine clinical assessment	

Outline any other processes that have been put in place to mitigate risks to participant safety (e.g. DMC, independent data review, etc.)

MHRA assessment of the trial protocol

Trial oversight committees

Independent protocol review

National Research Ethics Committee

Maximum dosing levels defined

Exclusion of patients at risk of adverse events e.g. patients with known history of seizures.

Advice that cefuroxime may affect the gut flora (as with most antibiotics), leading to lower oestrogen reabsorption and reduced efficacy of combined oral contraceptives.

## **16.2 Appendix 2 - Study management / responsibilities**

### **16.2.1 Patient registration/randomisation procedure**

No part of the trial coordination is outsourced.

### **16.2.2 Data management**

No outsourcing of data management is planned.

The PI is responsible for data management.

CRF will be data checked, and the online database will facilitate this process.

### **16.2.3 Preparation and submission of amendments**

No part of the trial coordination is outsourced.

### **16.2.4 Preparation and submission of Annual Safety Report/Annual**

No part of the trial coordination is outsourced.

### **16.2.5 Data protection/confidentiality**

No part of the trial coordination is outsourced.

### **16.2.6 Trial documentation and archiving**

No part of the trial coordination is outsourced.

## **16.3 Appendix 3 – Authorisation of participating sites**

Not applicable: single site study.

### 16.4 Appendix 4 – Schedule of Procedures

Time (Specify months/ weeks/ days)		0	Day 5	Day 8-30		30 days	
	Preoperative/Pre-assessment clinic*	Surgery	Day 5 (+/- 48 hours) or earlier if discharge at less than 5 days.	72 hourly post initial assessment	Discharge	30 days post surgery/End of trial	Premature withdrawal
Informed consent	X						
Assessment of Eligibility Criteria	X						
Review of Medical History	X		X	X	X	X	
Review of Concomitant Medications	X						
Registration	X						
Physical Exam - Complete			No	No	No	No	
Physical Exam - Surgical site			X	No	No	No	
Documentation of surgical practices e.g. antibiotic prophylaxis		X					
Review of clinical notes including antibiotic prescribing	X		X	X	X	X	
Patient questionnaire	X		X			X	
Height	X						
Weight	X						
Heart rate, respiratory rate, blood pressure							
Rectal swab	X						
Wound swab							
Study intervention (antibiotics) and documentation of surgical practices		X					
Assessment of Adverse Events			X	X	X	X	X

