##### **Antibiotic prophylaxis to prevent SSI – current practice and limitations.**

In an attempt to prevent SSIs antibiotics are usually given just before an operation, this is called antibiotic prophylaxis. Antibiotic prophylaxis is effective. When initially introduced antibiotic prophylaxis reduced SSI rates from 40% to 10% (Nelson 2014). Currently, published evidence suggests SSI rates after elective colorectal surgery occur in over > 10% of patients (Kirby 2015a, Petrosillo 2008, Smith 2004, Tanner 2009, Wick 2008). The reasons for the higher rate of SSIs now are unclear, but it may represent different definitions (SSI includes organ space infections, SSI does not), more aggressive treatment e.g. pre-operative radiotherapy, or that antibiotic prophylaxis is less effective. In patients undergoing emergency procedures SSI rates are higher than for elective procedures (Morikane 2014). Most SSIs (90%) occur within 14 days of the operation (Kirby 2015a). These infections are commonly caused by bacteria that live in the human bowel. The types of bacteria from the bowel which are believed to cause SSIs are called Enterobacteriaceae, commonly referred to as “coliforms” (e.g. *E. coli*) and anaerobes.

Antibiotic prophylaxis is currently prescribed to patients at doses similar to those used to treat infections such as pneumonia. It is not known if these are the best doses to prevent infections after colorectal surgery. There has only been one study which compared different antibiotic doses for the

prevention of SSI after colorectal surgery. In this study two different-dosing regimens were compared (Gentamicin: 4.5mg/kg and 1.5 mg/kg) in 146 patients. The study determined that the higher dose regimen had a lower SSI rate (22%) than the low dose regimen (55%) (Zelenitsky 2000). Unfortunately other studies have not been completed to further investigate if new, non-treatment based dosing regimens, are better at preventing post-operative SSIs when compared to dosing used for the treatment of infections.

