### 3.3 Outcome measures/endpoints

#### 3.4 Primary endpoint/outcome

Primary endpoint: Surgical site infection within 30 days of operation.

Endpoint aggregation by percent.

Timings of measurement: Day 5, Day 30.

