#### Post operative assessment-Visit 3, day 5 (approximately) post-operation, or day of discharge

- Medical history
- Antibiotic history
- Surgical site assessment: Where possible the surgical wound will be inspected and an SSI specific evaluation will be completed
- Infections assessed as per standard (HPA point prevalence survey) definitions

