#### Post-operative assessments-Visit 4 (4A, 4B etc) (72 hourly post visit 3 while in-patient)

- Medical history
- Antibiotic history
- Surgical site assessment: Where possible the surgical wound will be inspected and an SSI specific evaluation will be completed
- Infections assessed as per standard (HPA point prevalence survey) definitions

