## 11 DATA HANDLING

### 11.1 Data collection tools and source document identification

Data collection will be by paper case report forms (CRFs)

CRFs will be created to document

- Surgical history, including antibiotic prophylaxis and blood collection timings
- Day 5 surgical site infection assessment
- Post operative medical history including antibiotic consumption within 30 days of surgery, infection diagnoses and length of hospital stay
- End of study form including mortality data
- Quality of Life questionnaires (EQ5-D)
- Surgical site infection questionnaire.

Records of all participating patients (sufficient information to link records e.g., CRFs, hospital records and samples), all original signed informed consent forms and copies of the CRF pages will be kept.

Records will be stored in a locked room at the Old Medical School, Leeds General Infirmary, Leeds.

All research forms will be labelled with a patients study number.

To maximise data collection, telephone assessments and postal questionnaires will be used where patients are unable to attend in person for assessments.

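### Appendix 4 rules out wound examination at the 72-hourly in-patient visits where section 7.7 plans it, and section 3.4 and the CRF list follow Appendix 4

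*Combined protocol and SAP*

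**What the plan says.** Four places in the protocol bear on when the wound is examined.

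- **Appendix 4 (section 16.4).** The row "Physical Exam - Surgical site" has an X in the column headed "Day 5 (+/- 48 hours) or earlier if discharge at less than 5 days". The 72-hourly, discharge and 30-day columns each say *No*. For the 72-hourly visits the schedule keeps medical history, notes review and adverse events.
- **Section 7.7.** Visit 3 is headed "Post operative assessment-Visit 3, day 5 (approximately) post-operation, or day of discharge". Visit 4 follows "72 hourly post visit 3 while in-patient", and its list of assessments includes: "Where possible the surgical wound will be inspected and an SSI specific evaluation will be completed". Visit 5, from day 30, is normally done by post or telephone.
- **Section 3.4.** The endpoint is SSI within 30 days, with "Timings of measurement: Day 5, Day 30".
- **Section 11.1.** The CRF list names a "Day 5 surgical site infection assessment", a post-operative history form that takes infection diagnoses, and an SSI questionnaire. It names no wound-assessment form for later in-patient visits.

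The endpoint rationale after section 3.4 concedes that the SSI criteria rest partly on the assessor's judgement of the wound, and relies on a training package to standardise it. The Background limits SSI in this study to superficial and deep infection, leaving out organ-space infection.

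**The concern.** The same in-patient visits carry opposite instructions for assessing the primary endpoint. Research staff usually work from the schedule table and the CRFs, and here both point away from section 7.7. It cannot be assumed that section 7.7 will be followed.

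What is at stake is how an SSI is established in a patient who stays in hospital beyond the day-5 visit. Under section 7.7 a trained assessor looks at the wound every 72 hours where that can be done. Under Appendix 4 the trial depends on what ward staff wrote down or what the patient later reports. For an endpoint confined to superficial and deep infection, and judged partly by eye, that is weaker ascertainment. If some staff follow one passage and some the other, ascertainment will also vary from patient to patient. A missed inspection cannot be recovered once the visit has passed.

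**Working it through.** The plan states no figure on this point, so there is none to reproduce. The check is textual.

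**1. Are these the same visits?** Visit 3 is at about day 5 and Visit 4 begins 72 hours later: day 5 + 3 days = day 8. Appendix 4 heads the corresponding block day 8 to 30 and labels the column 72-hourly. They are the same visits.

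**2. Is the *No* deliberate?** The cell is filled, not blank. The row above, for the complete physical examination, has *No* in all four post-operative columns. The surgical-site row differs from it only at day 5. That is consistent with a single planned wound examination. The amendment history records changes to adverse-event reporting and dosing only, so it does not explain the difference.

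**3. The places side by side**

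| Time | Section 7.7 | Appendix 4 | Section 3.4 | Section 11.1 |
|---|---|---|---|---|
| Day 5 | Inspection and SSI evaluation, where possible | X | Listed | Form listed |
| 72-hourly, in hospital | Inspection and SSI evaluation, where possible | *No* | Not listed | No repeat wound form |
| Discharge after Visit 3 | No separate visit | *No* | Not listed | None |
| Day 30 | Post or telephone as a rule | *No*, questionnaire marked | Listed | Questionnaire |

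The contradiction lies in the 72-hourly row. There, section 7.7 stands alone against three places that omit the inspection, one of them explicitly. The discharge and day-30 rows are not in conflict.

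**4. Can the affected events be counted?** The number of SSIs that lose direct inspection is the product of:

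- expected SSIs: at the section 10.1 rates and 45 per arm, 45 × 0.165 + 45 × 0.0825 = 7.4 + 3.7 = 11.1;
- the share arising after the last scheduled examination: not given. The Background says "Most SSIs (90%) occur within 14 days of the operation", which fixes at least 10% after day 14 but nothing at day 5. The examination itself may fall anywhere from day 3 to day 7, or earlier at discharge;
- the share of those arising in patients still in hospital at a Visit 4: not given, because length of stay is not stated.

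Two of the three factors are missing, so the product is not determined. A further unknown is how many of these events notes review would find anyway.

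**The case against.** The strongest reply is that the effect may be small. Visit 4 exists only for patients still in hospital. Anyone discharged by Visit 3 has no Visit 4, and later SSIs in those patients are normally found by post or telephone whichever passage governs. Appendix 4 also does not leave later in-patient SSIs unrecorded. History, notes and adverse events are still reviewed, a CRF takes infection diagnoses, and section 9.3 lists SSI among the expected adverse events. Section 7.7 is itself qualified by what is possible. All of this stands, and it limits the point to the loss of direct, standardised inspection in longer-stay patients. It does not remove the contradiction.

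Three stronger readings are tempting, and the documents do not support them.

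- **A count of missed events.** A reader might take the 90% by day 14 and assume an onset curve. With exponential onset the rate is ln(10)/14 = 0.1645 per day, so exp(−0.1645 × 5) = 44% arise after day 5. With uniform onset over 14 days it is 1 − 0.9 × 5/14 = 68%. Multiplied by 11.1 these give about 4.9 to 7.5 events. But the curves are assumptions, and the figure counts every SSI after day 5 wherever the patient is. It does not measure what this conflict affects.
- **A control rate that is too low for the full study.** Section 10.1 bases the full sample size on 16.5%, taken from elective patients. It does not say that the pilot's observed rate will replace it.
- **Different ascertainment in the two arms.** Section 7.4 has blinded outcome assessors and keeps the allocation out of the medical and anaesthetic notes. Nothing in the text shows that the conflict acts differently by arm.

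**Conclusion.** The point holds as an internal contradiction about how the primary endpoint is ascertained. Confidence in the textual conflict is high. Its consequence depends on staff following the schedule and forms instead of section 7.7. In that case, SSIs arising after about day 5 in patients still in hospital lose direct inspection and rest on notes, recorded diagnoses or the day-30 questionnaire.

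The size is unknown, and no event count should be attached to it. Even so, with about 11 SSIs expected at the planning rates, a small number of differently classified cases would be a visible part of the total. The passages should be reconciled before recruitment proceeds on the present schedule and forms.

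**What to change.** Align the other three places with section 7.7:

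1. In Appendix 4, surgical-site row, change *No* to *X (if in-patient, where possible)* in the 72-hourly column.
2. In section 3.4, add the in-patient Visit 4 assessments to the measurement times, beside day 5 and day 30.
3. In section 11.1, make the day-5 SSI assessment a repeat form completed at each Visit 4, with a box for inspection not possible.
4. State that the same assessment times and form apply in both arms.

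The cost is wording in one table and two sections, plus a reusable form. The inspections add no procedure beyond what section 7.7 already plans. A separate examination at discharge is not part of this fix: section 7.7 has none for patients who stay past Visit 3, so it would be a new procedure to be justified on its own merits.

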**16.6 Appendix 5 – Amendment History**

Amendment No.	Protocol version no.	Date issued	Author(s) of changes	Details of changes made
1	1.1			AE/SAE event reporting updated
2	2.1		AK	Dosing regimen updated
3	2.2	10/101/2016	AK	Dosing regimen returned to original regimen

Protocol amendments will be submitted to the Sponsor for approval prior to submission to the REC committee.
